1.3 Secondary Objectives

- To compare the PFS of sacituzumab govitecan with pembrolizumab to that of sacituzumab govitecan alone in the subgroup of patients with PD-L1-positive HR+ / HER2- MBC.
- To compare the efficacy of sacituzumab govitecan with pembrolizumab to that of sacituzumab govitecan alone by assessing other clinical outcome measures, including overall survival (OS), objective response rate (ORR) by RECIST 1.1, duration of response (DOR), time to objective response (TTOR), time to progression (TTP), and clinical benefit rate (CBR), in all-comers (regardless of PD-L1 status) and in the subgroup of patients with PD-L1-positive HR+ / HER2- MBC.
- To evaluate the safety and tolerability of sacituzumab govitecan and pembrolizumab compared to sacituzumab govitecan alone by monitoring adverse events, including immune-related adverse events.

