7.1 Adverse Events List

7.1.1 Expected Adverse Events for Pembrolizumab

In the pembrolizumab monotherapy trials (P001/P002, P012, P013, and P028, plus the P011 monotherapy arm), the overall incidence of AEs ranged from 83.0% (73 of 88 subjects in P012) to 100% (10 of 10 subjects in P011). The most commonly reported AEs included fatigue, diarrhea, decreased appetite, nausea, and anemia. The incidence of drug-related AEs (DRAEs) ranged from 39.8% (35 of 88 subjects in P013) to 80.0% (8 of 10 subjects in P011). The most commonly reported DRAEs across all studies were nausea, fatigue, and diarrhea. The incidence of Grade 3-5 DRAEs across studies ranged from 6.8% (6 of 88 in P013) to 12.0% (187 of 1562 subjects) in P001/P002. The most commonly reported Grade 3-5 DRAEs were anemia, elevated alanine aminotransferase, and elevated aspartate aminotransferase. Most subjects who experienced an AE continued in the study: the incidence of AEs leading to discontinuation ranged from 1.9% (8 of 430 subjects in P028) to 12.3% (192 of 1562 subjects in P001/P002). The majority of AEs leading to discontinuation were not considered to be related to pembrolizumab. Discontinuations due to a DRAE were infrequent and ranged from 0% (no subjects in P011) to 4.5% (4 of 88 subjects in P013). The most commonly reported DRAEs leading to discontinuation were pneumonitis, elevated alanine aminotransferase, and elevated aspartate aminotransferase.

List of AEs considered expected:

- Cardiac disorders: Myocarditis
- Endocrine disorders: Adrenal insufficiency, Hyperthyroidism, Hypophysitis, Hypopituitarism, Hypothyroidism, Secondary adrenal insufficiency, Thyroid disorder
- Eye disorders: Uveitis
- Gastrointestinal disorders: Abdominal pain, Colitis, Diarrhea, Pancreatitis
- General disorders and administration site conditions: Asthenia, Pyrexia
- Hepatobiliary disorders: Autoimmune hepatitis, Hepatitis, Sclerosing cholangitis
- Infusion related reaction
- Metabolism and nutrition disorders: Diabetic ketoacidosis, Hyponatremia, Type 1 diabetes mellitus
- Musculoskeletal and connective tissue disorders: Arthralgia, Back pain, Myositis, Vasculitis
- Nervous system disorders: Guillain-Barré syndrome, Myelitis
- Renal and urinary disorders: Nephritis
- Respiratory, thoracic and mediastinal disorders: Cough, Pneumonitis
- Skin and subcutaneous tissue disorders: Pruritis, Rash, Severe skin reaction, Vitiligo

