7.1.2 Expected Adverse Events for Sacituzumab Govitecan

The safety profile of sacituzumab govitecan was initially characterized based on 420 patients included in the overall safety population in the IMMU-132-01 study. These patients were treated with doses of 8 mg/kg, 10 mg/kg, 12 mg/kg, and 18 mg/kg. This population included 164 patients with breast cancer (including 108 patients with metastatic triple negative breast cancer treated with

10 mg/kg), 45 patients with urothelial cancer, 110 patients with lung cancer (small cell lung cancer and non-small cell lung cancer), and 101 patients with other epithelial cancers (including cervical, colorectal, endometrial, epithelial ovarian, esophageal, gastric, glioblastoma multiforme, head and neck, hepatocellular, prostate, pancreatic, and renal). The mean treatment duration in these patients was 160 days (7.7 cycles). The following is a summary of the safety profile; additional details can be found in the Investigator's Brochure.

Nearly all patients experienced at least one adverse event; approximately 75% of patients experienced one \geq NCI CTCAE Grade 3 AE; 41% experienced one or more SAEs. The protocol provided instructions for dose reduction and interruption, and treatment discontinuation based on toxicities. AEs led to treatment interruption in 48% of patients; however, only 11% of patients discontinued due to adverse events. Fatal adverse events (within 30 days of last dose) occurred in 6.7% of patients; however nearly all of these deaths were in the setting of disease progression.

The most frequent adverse events were gastrointestinal (nausea, vomiting, and diarrhea) and myelosuppressive (neutropenia and anemia). Nausea occurred in 67% (5% \geq Grade 3); vomiting occurred in 44% (4% \geq Grade 3), and diarrhea occurred in 62% (9% \geq Grade 3) of patients. All patients were administered prophylactic antiemetic treatments and nausea, vomiting, and diarrhea were managed according to standard treatment guidelines. With aggressive management of these toxicities, few patients required treatment discontinuation.

The most frequent myelosuppressive adverse events were neutropenia (41%, \geq Grade 3 28%) and anemia (41%, \geq Grade 3 11%). Neutrophil count decreased occurred in 18% of patients (13% \geq Grade 3) and febrile neutropenia occurred in 6%. Although treatment was interrupted due to neutropenia in 21% of patients, only one patient discontinued due to this toxicity.

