13 STATISTICAL CONSIDERATIONS

13.1 Study Design/Endpoints

This is a randomized phase II open label study of sacituzumab govitecan +/- pembrolizumab for patients with HR+ / HER2- MBC. Sacituzumab govitecan will be administered at a dose of 10 mg/kg IV on days 1 and 8 of each 21-day cycle, and pembrolizumab will be administered at a dose of 200 mg IV on day 1 of each 21-day cycle. The target enrollment is 110 patients; 55 per arm of treatment.

The primary endpoint is PFS defined as the time from study randomization to disease progression, per RECIST 1.1 or medical judgment, the latter based on established clinical parameters, such as rising tumor markers and physical exam evidence of progression, i.e., worsening chest wall disease, or death due to any cause, whichever occurred first. Patients alive without disease progression are censored at the date of last disease evaluation. The primary objective is to compare in the intent-to-treat (ITT) population (as defined in Section 13.5) the PFS in patients randomized to receive sacituzumab govitecan in combination with pembrolizumab (Arm A) versus those randomized to receive sacituzumab govitecan monotherapy (Arm B).

Secondary endpoints include:

- PFS according to RECIST 1.1 in the PD-L1-positive population (defined as CPS ≥ 1)
- Overall response rate (ORR) according to RECIST 1.1 in the ITT and PD-L1+ population
- Overall survival (OS) in the ITT and PD-L1+ population
- Clinical benefit rate (CBR) according to RECIST 1.1, defined as CR, PR or stable disease for ≥ 24 weeks in the ITT and PD-L1+ population
- Time to progression (TTP) in the ITT and PD-L1+ population
- Duration of response (DOR) and time to objective response (TTOR) in the ITT and PD-L1+ population
- Toxicity graded according to NCI CTCAE, Version 5.0

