13.6 Analysis of Secondary Endpoints

Efficacy Endpoints

- Among patients who initiated protocol therapy and whose tumor was centrally confirmed to be PD-L1-positive (as defined by CPS ≥ 1 using the PharmDx 22C3 assay), the efficacy, as assessed by PFS, of sacituzumab govitecan plus pembrolizumab will be compared to sacituzumab govitecan alone. PD-L1 status will be defined by central confirmation of PD-L1 testing on the baseline research biopsy, if available; if not available, then the central PD-L1 testing results from the archival sample will be used. The comparison of PFS between treatment arms in the PD-L1-positive subgroup will be exploratory.
- In the modified ITT and PD-L1-positive population, all patients who initiated protocol therapy will also be evaluated for ORR (according to RECIST 1.1), CBR, DOR, TTOR and OS.

Radiographic response will be assessed using RECIST 1.1 criteria, as defined in section 11. Objective response will require confirmatory scans or exam as indicated. The ORR (CR + PR), according to RECIST 1.1, will be reported with 95% confidence intervals. Clinical benefit is defined as CR, PR or SD ≥ 24 weeks according to RECIST 1.1 and will be reported with 95% confidence intervals. Median DOR and TTOR will be reported with ranges. Overall survival, defined as the time from randomization (or registration) to death due to any cause with censoring at date last known alive, will be reported with Kaplan Meier estimates.

For OS, the log-rank test will be one-sided. Treatment efficacy in these secondary endpoints will be assessed by Cox models adjusting for clinical factors such as age at study entry, stage (locally advanced or metastatic), visceral metastases (yes or no), level of ER expression (1-9% vs. 10% or greater), and rapid recurrence after completion of adjuvant therapy < 6 months (yes or no). Dichotomous endpoints of response will be compared using Cochran-Maentel-Haenszel chi-squared tests.

Safety and tolerability

All patients will be evaluable for toxicity from the time of their first treatment with any study agent. Toxicity will be graded according to NCI CTCAE, Version 5.0. Toxicities will be summarized by maximum grade and by treatment arm. Incidence rate of each toxicity will be reported with 95% confidence intervals. The incidence rates of any grade 3 or higher toxicity will be compared across arms using a two-sided Fisher's exact test.

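### The one planned between-arm toxicity test has about 3–4% power (independent toxicities) or 9–27% (no overlap) at the pembrolizumab rates the protocol cites, and no immune-related comparison is planned

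*Combined protocol and SAP*

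**What the plan says.** - The safety objective (Section 1.3) is to evaluate the combination against sacituzumab alone "by monitoring adverse events, including immune-related adverse events".
- Section 13.6 tabulates toxicities by worst grade and arm and gives each toxicity a rate with a 95% interval. It names one between-arm test: "The incidence rates of any grade 3 or higher toxicity will be compared across arms", using a two-sided Fisher's exact test. It gives no alpha, power or detectable difference, and does not say whether toxicity means all-cause or treatment-related.
- Section 13.1: "The target enrollment is 110 patients; 55 per arm of treatment".
- Section 7.1.2, on 420 sacituzumab patients with mixed tumours: "Nearly all patients experienced at least one adverse event; approximately 75% of patients experienced one" or more grade 3+ events. On dose: "These patients were treated with doses of 8 mg/kg, 10 mg/kg, 12 mg/kg, and 18 mg/kg".
- Section 7.1.1, on pembrolizumab monotherapy: "The incidence of Grade 3-5 DRAEs across studies ranged from 6.8% (6 of 88 in P013) to 12.0% (187 of 1562 subjects" in P001/P002).
- Follow-up differs by drug. Section 7.2 requires SAE reporting for 30 days after the last dose, and for 90 days with pembrolizumab. Footnote p of the Study Calendar (Section 10) limits the 90-day adverse-event assessment to Arm A.

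**The concern.** Both arms receive sacituzumab on the same schedule, so the arms differ only by pembrolizumab. A composite of any grade 3+ event is a blunt measure of that difference: a patient already counted for grade 3 neutropenia adds nothing if severe hepatitis follows. The events the objective singles out, immune-related ones, are not grouped or compared anywhere in Section 13.

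What is at stake is interpretation. A non-significant p-value from the only named toxicity test could be taken as showing little added harm, when the test had little chance of detecting harm of the size the protocol itself cites. An immune-event comparison added later would also be biased if Arm A is observed for longer after the last dose.

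**Working it through.** **The plan's own figures.** The documents give none for this test. The sizing behind 55 per arm does reproduce: for 100 PFS events, HR 0.65 and one-sided alpha 0.1, power = Φ(√100/2 × |ln 0.65| − 1.282) = Φ(2.154 − 1.282) = 0.81, against 80% stated. The trial was sized for PFS, not toxicity.

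**Inputs.** n = 55 per arm (13.1). Arm B rate p = 75% (7.1.2). Pembrolizumab grade 3+ rate r = 6.8–12.0% (7.1.1), with 16% from the 32-patient TNBC cohort (2.3.5) as a higher value. Two-sided alpha 0.05 is assumed. An r of 20% is hypothetical and appears nowhere in the documents.

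**Arm A rate.** If toxicities are independent: p + (1 − p) × r. If no patient has both: p + r. For r = 12%, these give 0.75 + 0.25 × 0.12 = 78.0% and 0.75 + 0.12 = 87.0%.

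**Exact power of the two-sided Fisher test** (enumerating both binomials):

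| r | Arm A, independent | Power | Arm A, no overlap | Power |
|---|---|---|---|---|
| 6.8% | 76.7% | 3.3% | 81.8% | 9.2% |
| 12.0% | 78.0% | 4.0% | 87.0% | 27.1% |
| 16% | 79.0% | 4.9% | 91.0% | 51.6% |
| 20% (hypothetical) | 80.0% | 6.1% | 95.0% | 80.1% |

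With no true difference the test rejects 3.0% of the time, so the independent column is close to the false-positive rate. Power reaches 80% only when Arm A is about 95%.

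**Sensitivity, r = 6.8–12.0%.**
- Alpha 0.10, independent: 6.8–8.0%.
- Arm B 65%: 3.8–5.1% independent, 8.5–22.0% no overlap.
- Arm B 50%: 3.8–6.1% independent, 7.1–17.7% no overlap.

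**A lower-background immune endpoint, same r, independent.** The documents give no Arm B rate, so a range is assumed:

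| Assumed Arm B rate | Power, r = 6.8% | Power, r = 12.0% |
|---|---|---|
| 2% | 15% | 49% |
| 10% | 9% | 25% |
| 15% | 8% | 19% |

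The choice of terms therefore matters. Table 4 (Section 6.2) and the list in 7.1.1 both include diarrhea, which is grade 3+ in 9% of sacituzumab patients in 7.1.2 and grade 3–4 in 8% in Table 3. A list containing it cannot have a 2% background.

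**Precision as an estimate.** The 95% half-width is 1.96 × √[pA(1 − pA)/55 + pB(1 − pB)/55]. For 78% against 75% it is 16 points around a 3-point difference. For 14% against 2% it is 10 points around a 12-point difference.

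**The case against.** The case against has several parts.

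- **A secondary test in a phase II trial need not be powered.** True, and low power alone is not an error here. What remains is that the objective names immune-related events and no analysis groups or compares them.
- **Per-toxicity rates by arm are planned.** So pneumonitis, colitis and hepatitis would be visible, and a reader who inferred that immune toxicity would be hidden would go too far. But those are single-arm rates, term by term. They give no difference between arms, and scattered immune events are not pooled.
- **Safety is watched elsewhere.** The run-in covers 12 Arm A patients for one cycle; DSMB review and exploratory PRO-CTCAE comparisons are also planned. None gives a between-arm estimate of severe immune toxicity.
- **The sentence may mean a test for each grade 3+ toxicity.** That reading is possible. It would leave the terms and multiplicity unspecified, with still no immune grouping, so the request stands.
- **The 75% is not a causal rate.** Correct. It counts patients who experienced events of any cause, across mixed tumours and pooled doses. A reader might infer that sacituzumab alone causes grade 3+ toxicity in 75% of patients; Section 7.1.2 does not say so.
- **Saturation is not the main driver.** Largely right. At the cited increments under independence, power is only about 4–6% even with a 50% background. The small increment and 55 per arm matter more. Background does matter against a rare-event endpoint: at r = 12%, 4% power on the composite and 49% at an assumed 2% base.

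**Conclusion.** The point holds in a limited form. At the pembrolizumab rates the protocol cites, the composite test has about 3–4% power if toxicities are independent and 9–27% if they never overlap. This assumes 55 per arm, two-sided alpha 0.05, a 75% Arm B rate and the composite reading. No overlap is the upper end unless the drugs potentiate each other. A non-significant result would be weak evidence about added toxicity. The immune-related part of objective 1.3 has no pooled endpoint or between-arm difference, and the two arms are not followed equally after the last dose.

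Two stronger conclusions are tempting but not supported:

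- **That non-significance is almost certain even with a 20% added rate.** This depends on independence. With no overlap, power there is 80%, and the documents do not cite a 20% rate.
- **That an immune-specific endpoint would be well powered.** At a 2% base, power is only about 15–50% for the cited rates, and lower at a higher base. Those rates also cover all drug-related grade 3–5 events, so the immune-only excess may be smaller.

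The case for change is a better-targeted estimate, not a powered test.

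**What to change.** In Section 13.6, report the between-arm risk difference with a 95% confidence interval for:

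1. grade 3+ events from a fixed immune-type term list drawn from Table 4 and Section 7.1.1, counted whatever the attribution. Leave terms common on sacituzumab (diarrhea, abdominal pain, asthenia, pyrexia) out of the main list and add them in a sensitivity version;
2. grade 3+ non-hematologic events;
3. SAEs;
4. events leading to discontinuation of sacituzumab.

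Use the same window after the last dose in both arms, for example truncated at 30 days, with later Arm A events listed separately. State whether toxicity means all-cause or related, and whether the Fisher test is on a composite or on each term. Keep the any-grade-3+ comparison as descriptive, and state that non-significance is not evidence of equal safety. Label the new results as estimates, not powered tests.

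Cost: analysis-plan wording and a few tables from data already collected (Section 7.8 requires routine reporting of grade 2 or higher events, other than laboratory values that are not clinically significant). The downside is a few more comparisons without multiplicity adjustment.

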13.7 Correlative Endpoints

13.7.1 Tumor biopsies and TIL assessment

Previous studies have demonstrated that, in addition to direct cytotoxic effects, chemotherapy-induced cell death can be immunogenic, causing T cell tumor infiltration and sensitizing tumors to immune checkpoint blockade.⁹⁸ Cytotoxic CD8+ T cell infiltration has been reported to increase after treatment with chemotherapy across different tumor types.⁹⁹⁻¹⁰¹ Recently, Herbst et al.

demonstrated that patients who had an increase of at least 5% in expression of PD-L1 in the tumor microenvironment were more likely to respond to the PD-L1 inhibitor atezolizumab.⁵⁸ Modifications in molecular signatures of the tumor microenvironment also correlated with response to therapy.

Tumor-infiltrating lymphocytes (TILs) by histological assessment will be quantitative and evaluated as a percentage of cells stained (0-100%). Data from Loi and colleagues suggest that the mean number of TILs in first-line HR+ / HER2- MBC is likely similar to that observed in first-line metastatic HER2-positive samples from the CLEOPATRA study.¹⁰² The median TIL value was 10% with a mean number of TILs of 17% (standard deviation as a continuous variable of 21%). TILs will be analyzed as a continuous variable using descriptive statistics to summarize the distribution observed among study participants.

A) To assess the relationship between baseline TILs and progression-free survival, we plan to perform a mandatory research biopsy of a safely accessible tumor lesion at baseline. The association of TILs and PFS will be evaluated in a proportional hazards regression model with treatment effect and study stratification factors as covariates.¹⁰³ Linear and non-linear components of the model will be assessed using Wald-type tests. If a non-linear association is detected, the point estimate and 95% prediction bands will be reported for the log relative hazard over the entire distribution of TILs. If no significant non-linear effects are observed, the step-down model will evaluate the linear multivariate proportional hazards regression model and report the adjusted hazard ratio and 95% confidence interval for a linear increase in TILs. In addition, modification of the treatment effect will be explored as an interaction test, and if non-significant (two-sided alpha = 0.05), the step-down model with main effects will be reported.

B) To assess the absolute change in the percentage of TILs before and after starting treatment, a mandatory biopsy at 3-6 weeks post-treatment (any time between C2D1 and C3D1) is required, if tumor is safely accessible. This on-treatment biopsy will be performed in, at least, the first 27 patients with accessible disease in each arm. Assuming the drop-out/non-evaluable rate will be 10%, 24 paired samples will be available.

Descriptive statistics will be used to summarize the distribution of TILs observed at baseline and after 3-6 weeks of therapy (e.g., mean, standard deviation, median, and inter-quartile range). The evaluation of change in TILs within each arm will be based on a paired t-test (absolute difference) using a one-sided alpha = 0.05 for each arm. Based on the variability of TILs reported by Loi and colleagues in paired specimens before and after treatment with chemotherapy for TNBC, with 24 evaluable paired specimens anticipated per arm and a standard deviation of eight, there will be 82% power to detect an increase in mean TILs from 22.3% to 26.5%, under an assumption of an additive shift model with a Gaussian common density function.

If paired biopsies at baseline and at 3-6 weeks after treatment are obtained in 24 paired samples in each arm (assuming a drop-out/non-evaluable rate of 10% in the entire study population), there will be statistical power to detect the following change in TILs between both study arms. Assuming that the mean difference in TILs from pre-treatment to 3-6 weeks after starting protocol therapy is 10.4% in Arm A (sacituzumab govitecan + pembrolizumab) and 4.2% in Arm B (sacituzumab govitecan alone), with a standard deviation of 8, using a Wilcoxon-Mann-Whitney test with one-

sided alpha of 0.05, the study has 80% power to detect the difference of change in TILs between Arm A (sacituzumab govitecan + pembrolizumab) and Arm B (sacituzumab govitecan alone).

Optional repeat biopsies will be performed at time of progression to explore changes in TILs and other tissue markers. Descriptive statistics will be used to summarize the change in TILs, and inferences on treatment-effects will use non-parametric tests (e.g., Wilcoxon rank sum) with two-sided alpha 0.05. The association of changes in TILs with clinical outcomes of PFS and OS will be exploratory and hypothesis generating in the subset of patients with evaluable repeat biopsies. Analysis plans will consider using Cox models with time-varying covariates to account for the post-baseline assessments.

C) For secondary correlative endpoints to characterize the expression of tumor markers by immunohistochemistry (IHC) and/or immunofluorescence (IF), descriptive statistics and agglomerative hierarchical clustering techniques will be used to summarize the distribution and patterns of profiles observed in baseline samples. Tests of association with clinical outcomes (PFS, OS, ORR) will be exploratory using Cox proportional hazard and logistic regression models, and inferences will use the Benjamini-Hochberg method to control the false discovery rate. Any positive findings will require validation in future studies with independent samples for unbiased estimates of the association with treatment effects and clinical outcomes.

Efficacy endpoints will be analyzed according to Trop-2 expression, which will be evaluated as percent of positive cells, intensity, a composite score, or another method. Analyses of Trop-2 expression are descriptive and exploratory in nature and intended to examine the distribution of Trop-2 expression levels at different biopsy sites and assess associations between Trop-2 expression and efficacy outcomes, such as PFS, OS and ORR, for which separate analyses will be performed according to Trop-2 expression (above and below median) and treatment group.

D) Single-cell RNA sequencing will be performed on biopsies at baseline, on treatment, and, when available, at progression for a subset of patients enrolled at DFCI to assess the relationship of timepoint-specific tumor and immune cell subpopulations with clinical outcomes in exploratory analyses. In addition, changes in single-cell RNA expression signatures across these timepoints will be correlated with response. Standard preprocessing and quality control algorithms will be performed to filter out low quality cells and to normalize the expression data. Differentially expressed genes will be identified using the Benjamini-Hochberg procedure to control the false discovery rate for multiple comparisons. Descriptive statistics and clustering techniques, including principal component analysis and t-distributed stochastic neighbor embedding, will be employed to summarize the distributions of the expression data and identify tumor and immune cell subpopulations. Changes in cell subpopulations between baseline, on-treatment, and at progression biopsies will be assessed with Wilcoxon signed-rank tests, while differences in cell subpopulations between responders and non-responders will be compared with Mann-Whitney tests. Preliminary associations of tumor and immune cell subpopulations with progression-free and overall survival will be explored using Cox proportional hazard models.

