1 OBJECTIVES

1.1 Study Design

This is a randomized phase 2 open label study of sacituzumab govitecan +/- pembrolizumab for patients with hormone receptor-positive (HR+) / HER2- metastatic breast cancer (MBC). Patients will be randomized in a 1:1 ratio to sacituzumab govitecan (IMMU-132) with pembrolizumab (Arm A) or sacituzumab govitecan alone (Arm B) and will be treated until unacceptable toxicity or progression as defined by RECIST 1.1 criteria.

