1.4 Correlative/Exploratory Objectives for Enrolled Participants

- 1.4.1 To explore tissue biomarkers of antitumoral immune activity and tumor genomic instability as predictors of response and resistance to sacituzumab govitecan plus pembrolizumab compared to sacituzumab govitecan alone in patients with HR+ / HER2- MBC.
- To characterize baseline Trop-2 expression by histological assessment and correlate with disease response to treatment (PFS, ORR by RECIST 1.1, OS).
 - To assess changes in Trop-2 staining, from baseline to on-treatment and at-progression, and correlate with disease response to treatment (PFS, ORR by RECIST 1.1, OS).

- To characterize tumor-infiltrating lymphocytes (TILs), by histological assessment, at baseline and correlate with disease response to treatment (PFS, ORR by RECIST 1.1, OS).
 - To characterize the expression of markers of immune cell subsets (i.e., CD8 for cytotoxic T cells, CD68 for macrophages), inhibitory checkpoint pathway molecules (i.e., PD-1, PD-L1, TIM3, LAG3), and co-stimulatory pathway molecules (i.e., GITR, OX40) by immunohistochemistry (IHC) and/or immunofluorescence (IF).
 - To explore whether immunosuppressive and/or immune-stimulating immune marker profiles at baseline correlate with disease response to treatment (PFS, ORR by RECIST 1.1, OS).
 - To characterize mutational load and neoantigen burden at baseline and correlate with disease response to treatment (PFS, ORR by RECIST 1.1, and OS).
 - To characterize RNA expression signatures of immune pathway activation and DNA damage repair deficiency at baseline and correlate with disease response to treatment (PFS, ORR by RECIST 1.1, and OS).
 - To explore whether changes in TILs, immunosuppressive and/or immune-stimulating immune marker profiles, mutational load, neoantigen burden, and RNA expression signatures, between paired biopsies from baseline and after 2 cycles of treatment, correlate with disease response to treatment (PFS, ORR by RECIST 1.1, OS).
 - To explore mechanisms of resistance to sacituzumab govitecan plus pembrolizumab compared to sacituzumab govitecan alone in paired biopsies from baseline and at time of progression.
 - To explore whether the number and/or type of mutations identified using a next generation sequencing (NGS) panel is correlated with patient outcomes (PFS, ORR by RECIST 1.1, and OS). This will be performed on DFCI participants only.

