13.2 Sample Size, Accrual Rate and Study Duration

Based on data of recent trials in a similar population of patients with metastatic breast cancer treated with sacituzumab govitecan, a median PFS of 5.5 months would be expected with sacituzumab govitecan monotherapy.³² Currently, there are no published data about the PFS of patients with HR+ / HER2- MBC treated with sacituzumab govitecan in combination with anti-PD-1 therapy. We anticipate that achieving a PFS of at least 8.5 months for combination therapy (Arm A) in the present study would make the regimen worthy of further investigation. Considering a one-sided 0.1 type-I error and 80% power to detect a 3-month absolute difference in median PFS at the time of final analysis (hazard ratio = 0.65), 110 patients would need to be enrolled on the trial.

The final analysis will occur when 100 PFS events are observed, or 2 months after the last patient is randomized, whichever occurs first. An interim analysis for futility will occur when $\sim 50\%$ of the information is obtained (50 PFS events). The study would stop early if the Z-statistic from a log-rank test is less than 0. It is estimated that the interim analysis will occur approximately 18 months after the first patient is randomized.

The expected accrual rate is 4-5 patients per month, with accrual of 110 patients anticipated to be completed at 24 months. The expected study duration to primary analysis of PFS is 2.5 to 3 years.

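### The TIL analysis falls back to a main-effects model when the arm-by-TIL interaction is not significant, with no commitment to report the interaction estimate and its interval

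*Combined protocol and SAP*

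**What the plan says.** Section 13.7.1 A) relates baseline TILs to PFS in a "proportional hazards regression model with treatment effect and study stratification factors as covariates". It then adds that "modification of the treatment effect will be explored as an interaction test", and that, "if non-significant (two-sided alpha = 0.05), the step-down model with main effects will be reported". For the linear TIL effect the same paragraph promises an adjusted hazard ratio with a 95% confidence interval. It makes no matching promise for the interaction.

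Objective 1.4.1 frames the tissue work as a search for markers "as predictors of response and resistance to sacituzumab govitecan plus pembrolizumab compared to sacituzumab govitecan alone". Section 9 labels all blood and tissue biomarker analyses exploratory.

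**The concern.** A marker that predicts benefit from adding pembrolizumab shows itself as a TIL effect that differs between arms. The main-effects model forces that difference to zero and returns one TIL hazard ratio for everyone, which is prognostic information. If the rule is followed literally and the test misses 0.05, the reported model assumes away the quantity that the objective asks about.

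Two things are at stake. If power is low, the main-effects model will usually be the one reported, and a reader may take it as evidence that TILs do not modify the effect. If the interaction is highlighted mainly when significant, its size will on average be overstated, which matters for anyone who designs the next biomarker study from it.

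**Working it through.** **1. The plan's own figures.** Section 13.2 plans for "Considering a one-sided 0.1 type-I error and 80% power to detect a 3-month absolute difference in median PFS at the time of final analysis", at a hazard ratio of 0.65. Schoenfeld's formula gives 4(1.282 + 0.842)² / (ln 0.65)² = 97.2, so 98 events; 100 events give 80.8% power. The design reproduces. So does the paired TIL calculation in 13.7.1 B): √24 × 4.2 / 8 = 2.572, and Φ(2.572 − 1.645) = 82.3%, against 82% stated. That calculation, and the between-arm one that follows it, concern change in TILs. No power is stated for the interaction.

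**2. Inputs for the interaction.**
- Allocation: "Patients will be randomized in a 1:1 ratio" (1.1). Size: "The target enrollment is 110 patients; 55 per arm of treatment" (13.1).
- Covariates: 13.3 plans no stratification factors, so the model contains TILs, arm and their product.
- Test: two-sided 0.05 (13.7.1 A).
- TIL distribution: median 10%, mean 17%, "standard deviation as a continuous variable of 21"% (13.7.1). It is right-skewed.
- Events: 13.2.1 says that 100 PFS events will not be reached and puts the power loss from the earlier cut-off at about 5%. Read as 75% instead of 80% power, that corresponds to about 83 events: 4(1.282 + 0.674)² / (ln 0.65)² = 82.5. TILs exist only for patients with safely accessible tumor (3.1.5), and lung cores and bone biopsies are not done unless clinically indicated (9.2.2).
- **Assumed**, because the documents do not say: 40 to 80 PFS events among patients with a baseline TIL value (100 shown as a ceiling), and a true interaction hazard ratio of 0.65 to 0.80 per SD of TILs.

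**3. Formulas.** For a standardised marker and events split evenly between arms, SE = √(2/E + 2/E) = 2/√E. Let δ = |ln(ratio)| / SE and c = 1.96.
- Power = Φ(δ − c) + Φ(−δ − c).
- Average inflation given significance = [δΦ(δ − c) + φ(c − δ) − δΦ(−δ − c) + φ(c + δ)] / (δ × power).

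**4. One case in full: 60 events, ratio 0.80.** SE = 2/√60 = 0.258. The estimate must be exp(−1.96 × 0.258) = 0.60 or more extreme (or beyond its reciprocal) to be significant. δ = 0.223 / 0.258 = 0.864. Power = Φ(−1.096) + Φ(−2.824) = 0.139. Inflation = (0.118 + 0.219 − 0.002 + 0.007) / (0.864 × 0.139) = 2.85.

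**5. Range (power / average inflation on the log scale).**

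| Events | Ratio 0.50 | 0.65 | 0.75 | 0.80 |
|---|---|---|---|---|
| 40 | 59% / 1.3 | 28% / 1.9 | 15% / 2.7 | 11% / 3.4 |
| 60 | 77% / 1.1 | 39% / 1.6 | 20% / 2.3 | 14% / 2.9 |
| 80 | 87% / 1.1 | 49% / 1.4 | 25% / 2.0 | 17% / 2.5 |
| 100 | 93% / 1.0 | 58% / 1.3 | 30% / 1.8 | 20% / 2.3 |

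For 80% power the ratio per SD would have to be 0.41 at 40 events, or 0.57 at 100.

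**6. Skewed TILs.** The formula treats the marker as well behaved. A Cox simulation with gamma-distributed TILs (mean 17, SD 21, capped at 100; 1,500 runs per case) gave, for 40 to 80 events, 18% to 36% power with inflation of 2.9 down to 1.8 at ratio 0.65, and 10% to 15% with 4.9 down to 3.1 at ratio 0.80. Skew makes the position worse.

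**7. With unconditional reporting.** Selection on significance disappears. The 95% interval is roughly the estimate multiplied and divided by exp(1.96 × SE): 1.86 at 40 events, 1.66 at 60, 1.55 at 80. Skew widens it.

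**The case against.** The strongest reply is that the sentence selects a model and withholds nothing. It does not forbid giving the test result or the interaction estimate, and it does not spell out what is shown when the test is significant. A reader might infer that the interaction will be reported only when p < 0.05 and otherwise suppressed. The text does not go that far; what it lacks is a commitment.

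A second reply is that the interaction is a side question. The TIL item under 1.4.1 is about correlating baseline TILs with outcome, 13.7.1 A) opens with the relation between TILs and PFS, and the interaction comes as an addition. That is fair as to emphasis. Even so, the parent objective is comparative between arms, and only the interaction addresses the comparison.

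A third is that the work is exploratory and, for the IHC and IF markers in part C), positive findings must be validated in independent samples. The label limits the consequence, although the validation sentence does not formally cover part A). Nor does the label justify the rule, since exploratory work is done to supply estimates for later studies. For Trop-2, part C) already plans analyses by expression level and treatment group with no significance condition.

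**Conclusion.** The concern holds in a limited form. The model reported for TILs depends on the interaction p-value, and the plan does not commit to the estimate and interval that would answer its own comparative objective. With 40 to 80 events and a ratio of 0.65 to 0.80 per SD, both assumed, power is about 10% to 50% and a significant estimate is inflated about 1.4- to 3.4-fold. Inflation is larger with skewed TILs and slight if the interaction is very strong (1.1 to 1.3 at a ratio of 0.50).

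A reader might be tempted to quote a single inflation factor, such as two- to threefold, as a property of this trial. The documents do not support that, because they give neither the effect size nor the event count on which it depends. Nor does the point extend to the non-linearity step-down. That step is pre-specified, with bands over the whole TIL range if curvature is found, and a different functional form would be a matter of preference. A log scale, for instance, is undefined at 0% TILs.

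The effect is confined to exploratory biomarker conclusions. The primary and secondary endpoints are not touched.

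**What to change.** In Section 13.7.1 A), replace the clause that makes the reported model depend on the interaction test with:

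> The arm-by-TIL interaction ratio with 95% CI, and the TIL hazard ratio with 95% CI within each arm, will be reported whatever the p-value, as exploratory estimates. If a non-linear TIL term is used, the arm-specific log relative hazard curves with 95% bands will be reported instead.

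The main-effects model may be shown alongside. The interaction model is already fitted in order to run the test, so no new data or patients are needed. The price is that wide intervals appear in print: at 60 events, roughly the estimate multiplied and divided by 1.66. That width shows the reader how little the trial can say about TILs as a predictor.
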